7.4 Reporting Procedures

Any adverse event that is so determined, or reported otherwise to either the principal investigators or their designated research associates by the subject or medical staff caring for the subject and which meets the criteria for a new adverse event that is also attributable to the study will be documented as such.

7.5 Follow-up for Adverse Events

The Principal Investigator or designee will review all reported side effects up to 8 weeks after the patient's study (reviews done on a monthly basis) to assess adverse events.

7.6 Safety Monitoring

As noted in 7.2.

7. INTERVENTION DISCONTINUATION

Attributable adverse events will be reported to the IRB and the study suspended for discussion when needed.

8. STATISTICAL CONSIDERATIONS

9.1 General Design Issues

The proposed analytical plan will comprise 1) data cleaning and basic statistical analyses to identify potential outliers, assess for normality, and examine variation in each variable; 2) the generation of standard descriptive statistics summarizing the sample and its characteristics; and 3) statistical methods for analyzing each specific aim and hypothesis. For each aim, all calculated P values will be 2-sided and P<.05 will be considered statistically significant.

9.2 Primary Objective 1

To determine the differences in A β , cerebrovascular lesion load and brain structure in postmenopausal women who were treated with one of two mHTs vs. placebo after 13 years post-randomization and 9 years after the end of mHT administration phase.

Primary Hypothesis: Aβ PET SUVR (primary outcome), AV-1451 SUVR, WMH volume and regional cortical thickness (or hippocampal volume) are different in women who were treated with tE2 vs. placebo and oCEE vs. placebo.

Hypothesis 1a: Aβ PET SUVR (primary outcome), AV-1451 SUVR, WMH volume and regional cortical thickness (or hippocampal volume) differences in women who were treated with tE2 vs. placebo and oCEE vs. placebo are modified by the *APOE*e4 status (carrier/noncarrier).

Hypothesis 1b: Aβ PET SUVR (primary outcome), AV-1451 SUVR, WMH volume and regional cortical thickness (or hippocampal volume) differences in women who were treated with tE2 vs. placebo and oCEE vs. placebo during early post menopause are modified by the vascular disease risk at 13 years post-randomization.

Statistical Analysis for Aim 1: We will first summarize the data for Aim 1 using standard descriptive statistics and a variety of plots (histograms, scatterplots) to assess variable distributions. Our outcome measures: Aß PET SUVR (primary outcome), WMH volume, and regional cortical thickness (or hippocampal volume) for this aim will all be continuous crosssectional variables, we will use analysis of covariance (ANCOVA) to address the primary hypothesis. Treatment groups (tE2, oCEE, and placebo) will be included as the predictors of interest, coded so that placebo is the reference group. Standard methods (Least Significant Difference, Tukey's Honest Significant Difference, and Scheffé's test) will be used to assess pairwise differences. We will include a set of dummy variables to test and adjust for site (block) effects. The outcome variables will be transformed as necessary to meet regression assumptions underlying the ANCOVAs. These analyses will include baseline age, time from baseline, and APOE ε4 status (as appropriate) as covariates. We will test for interactions of treatment with APOE ε4 status through inclusion of two-way interactions in the models, and analyses in separate APOE £4 non-carrier and APOE £4 carrier strata. To address Hypothesis 1a, we will expand the set of covariates to include a vascular disease risk score assessed at the time of mHT/placebo initiation(82) or individual cardiovascular risk factors (systolic and diastolic BP, fasting glucose, smoking history, lipid profile, BMI, waist circumference). Possible interactions with these covariates will be handled in the same way as APOE ε4 status. Hypothesis 1b will be treated much the same way, but CVD risk scores will be constructed from data acquired at 13 years after initiation of mHT. Since some of the women in the study might have used mHT after the trial ended, we will perform a series of sensitivity analyses with and without those individuals to assess any important effects and ensure that the final conclusions are robust.

Power for Aim 1: Focusing on Florbetapir PET, our primary outcome variable for Aim 1, we first estimated the standard deviations in three groups of women (all subjects, APOE ε4 non-carriers, and APOE ε4 carriers) from the Mayo Clinic Study of Aging, a longitudinal study on aging and dementia. We identified women with an age range of 55-70 (mean age=65) similar to our projected sample, who underwent both Aβ PET imaging and APOE ε4 testing (n=264) Using

these standard deviations as estimates of variability in our projected sample, we estimated the minimum detectable effect sizes in the pairwise comparisons (using Cohen's d) with 80% power.

Table 3. Minimum detectable effect sizes for projected sample size and 80% power.

Comparison	All	APOE ε4 non-carriers	APOE ε4 carriers
oCEE vs. Placebo	0.308	0.358	0.619
tE2 vs. Placebo	0.312	0.355	0.665

These effect sizes fall in the medium (all and $APOE\ \epsilon 4$ non-carriers) to large ($APOE\ \epsilon 4$ carriers) range. In our 84 month KEEPS data, most of our observed Cohen's d values were close to 0.34 (all subjects), 0.37 ($APOE\ \epsilon 4$ non-carriers), and 1.18 ($APOE\ \epsilon 4$ carriers). We anticipate the effect sizes to be at least this large in the KEEPS Continuation study. Since the minimum detectable effect sizes in **Table 3** are close to or smaller than these values, we anticipate having adequate power to detect pairwise differences. We would expect similar effect sizes for the other outcomes.

9.3 Primary Objective 2

To determine the differences in longitudinal changes in cognitive performance and mood in postmenopausal women who were treated with one of the two mHTs vs. placebo.

Primary Hypothesis 2: Performance on four cognitive factors described in our bi-factor model and on POMS mood indices are different in women who were treated with tE2 vs. placebo and oCEE vs. placebo.

Hypothesis 2a: Cognitive and mood differences in women who were treated with tE2 vs. placebo and oCEE vs. placebo are modified by *APOE*e4 status (carrier/noncarrier).

Hypothesis 2b: Cognitive and mood differences in women who were treated with tE2 vs. placebo and oCEE vs. placebo are modified by the vascular disease risk at 13 years post-randomization.

Statistical Analysis for Objective 2: Analyses for this aim will focus on longitudinal cognitive outcome data collected over six predetermined and unequally spaced time points over a total period of 13 years. We will employ linear mixed-effects (LME) regression models with treatment groups (oCEE and tE2) vs placebo (and their interactions with time) as predictors of cognitive change, and baseline age, APOE ε4, and education as control variables as well as in APOE ε4 carriers and non-carriers separately. Separate models will be estimated for each of the cognitive factor scores and mood outcome measures. The cognitive factor scores include the following four domains: verbal learning and memory; auditory attention and working memory; visual attention and perceptual speed; speeded language and flexibility. The mood outcome will be measured with the Profile of Mood States (POMS). The LME model incorporates covariance structures to account for the correlation between repeated measures across time. The analyses for the LME model will be conducted using the limited information maximum likelihood complete sample approach to missing data. The incorporation of higher order terms in the mixed effect models will also be examined. All models will test and adjust for site effects. The shape of the trajectories across time will be inspected by plots and models will account for possible nonlinearity. Random effects will be evaluated by likelihood-ratio (χ 2) tests and fixed effects will be evaluated via F-tests based on Type III sums of squares. Quantile-quantile plots of residuals will also be examined for evidence of significant outliers. As in Aim 1, we will address Hypothesis 2a by adding to the models a vascular disease risk score assessed at the time of mHT/placebo initiation⁸⁴ or individual cardiovascular risk factors. Possible interactions with these covariates will be handled in the same way as APOE ε4 status. Similarly, for Hypothesis 2b we will derive CVD risk scores from data acquired at 12 years after initiation of mHT. Since some of the

women in the study might have used mHT after the trial ended, we will perform a series of sensitivity analyses with and without those individuals to assess any important effects and ensure that the final conclusions are robust.

Power for Objective 2: Power and sample size estimates to detect significant changes in cognitive function are based on Mayo Clinic pilot data collected over five unequally-spaced observation time points (0,18, 36, 48, and 84 months) with the verbal learning and memory factor as the longitudinal outcome and treatment groups vs. placebo as predictors. We assumed normally distributed continuous outcomes with missing data, two predictors (oCEE and tE2) with regression coefficients in factor score units for rate of change of, respectively, -0.20 and -0.11; a variance of 2.09 for the random intercept, a variance of 0.03 for the random slope, and a correlation between random slope and random intercept terms set to 0.07. Using a two-tailed α =0.05, a total sample size of 492 individuals will achieve a power of 82% to reject the hypothesis for this aim.

Alternative Strategy: We will evaluate our participants for incident MCI and dementia, but we do not expect to have sufficient power to test the differential progression to MCI or dementia in each of the mHT vs. placebo groups. However, we will explore this alternative approach if we have a sufficient number of incident cases.

9.4 Primary Objective 3

To determine the associations between imaging biomarkers investigated in Aim 1, and longitudinal changes in cognitive performance and mood investigated in Aim 2.

Primary Hypothesis 3: Higher Aβ (primary outcome), AV-1451 and WMH load, and smaller regional cortical thickness are associated with a longitudinal decline in cognitive performance since randomization

Statistical Analysis for Objective 3: Repeated cognition and mood measures will be available for time points ranging from trial baseline to 13 years post-baseline; we will use the same cognitive factor scores and POMS as in Aim 2. For each measure in Aim 2, we will consider the values at year 13, the changes in values from baseline to year 13, and predicted annual changes in values at year 13 (slopes). Aβ PET SUVR, WMH, and AD signature thickness and hippocampal volume will only be available at 13 years post-baseline. We will use plots and Pearson or Spearman correlation coefficients, as appropriate given the distributions of the variables involved, to describe and measure associations between cognitive/mood measures and imaging biomarkers. As in the previous aims, we will explore and include site and covariate effects through regression models, transform variables as needed to meet assumptions, and perform sensitivity analyses with and without individuals who continued to use mHT after the mHT administration phase ended.

Power for Objective 3: With 492 individuals and α =0.05, we will have 80% power to detect Pearson correlation coefficients as small as 0.127. In a linear regression, this would be an increase in the model R² due to the association of interest as small as 0.016. We should thus have sufficient power to detect small associations.

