1. STUDY OBJECTIVES

1.1 Primary Objectives

To assess effects of menopausal hormone therapy and normal aging on cognitive performance and imaging markers of brain structure in women approximately thirteen years after enrolling in the KEEPS trial. KEEPS participants were randomized to oral or transdermal estrogen treatments or placebo within three years of menopause. This is a follow up study of these women approximately thirteen years after randomization (9 years after study completion.) **No treatments are given as part of this study**; any current hormonal treatments are by choice and prescribed by the participant's personal physician.

Aim 1: Determine the differences in $A\beta$ and tau pathology of AD, cerebrovascular lesions and brain structure in women who were treated with either oCEE or tE2 compared to placebo during early post menopause.

Hypothesis 1: Aβ, tau, cerebrovascular lesions and brain structure are different in women who were treated with tE2 vs. placebo and oCEE vs. placebo during early post menopause, modified by the APOE ε4 status.

Aim 2: Determine the differences in longitudinal changes in cognitive performance and mood in women who were treated with either oCEE or tE2 compared to placebo within three years of menopause.

Hypothesis 2: The longitudinal change in cognitive performance and mood over 13 years in women treated with one of the two active estrogen formulations (tE2 or oCEE) will differ from longitudinal cognitive and mood changes occurring in women who received placebo, modified by the *APOE* ε4 status.

Aim 3: To determine the association between imaging markers investigated in Aim 1 and the change in cognitive performance investigated in Aim 2 eight to nine years after completing KEEPS trial participation.

Hypothesis 3: Higher $A\beta$, tau and WMH load, and smaller regional brain volumes are associated with a longitudinal decline in cognitive performance and mood outcomes since randomization.

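### Aim 2 leaves the form of time open until the data are seen and names no contrast for the 13-year change, so the Type III test of treatment by time may answer a different question

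*Combined protocol and SAP*

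**What the plan says.** Hypothesis 2 (section 1.1) asks whether "The longitudinal change in cognitive performance and mood over 13 years" differs between each active arm and placebo. The précis gives the split of that period: 4 years on study drug and 9 years afterwards.

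The analysis is in section 9.3 (Statistical Analysis for Objective 2). It starts from a linear mixed model with treatment and treatment by time, fitted to six unequally spaced visits. It then adds two openings: "The incorporation of higher order terms in the mixed effect models will also be examined" and "The shape of the trajectories across time will be inspected by plots and models will account for possible nonlinearity". Testing follows: "fixed effects will be evaluated via F-tests based on Type III sums of squares". Section 9.1 sets the threshold: "For each aim, all calculated P values will be 2-sided and P<.05 will be considered statistically significant".

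The plan does not give a polynomial order, knots, a selection criterion or a time origin. It does not say whether the plots are pooled or split by arm, or which contrast carries the hypothesis if time is not linear. Section 9.4 does list the year-13 value, the change to year 13 and the slope, but only for the associations in Aim 3.

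**The concern.** Study drug covers 4 of the 13 years, so a difference that builds up on treatment and then levels off or fades is plausible. A straight line cannot describe that pattern, and the plan rightly allows for other shapes. The gap is that it does not say what is tested once the shape changes.

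With treatment by time and treatment by time-squared both in the model, the Type III test of treatment by time refers to the slope difference where time equals zero. It changes with the choice of origin and is not the difference in 13-year change. Two analysts who both follow section 9.3 could report tests with the same name, on the same data, that point to different conclusions about a primary objective. There is also a selection issue: if the shape is chosen in response to how the arms differ, the test that follows no longer has its nominal error rate.

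**Working it through.** **The plan's own figure.** Section 9.3 says that "a total sample size of 492 individuals will achieve a power of 82% to reject the hypothesis for this aim", with "regression coefficients in factor score units for rate of change of, respectively, -0.20 and -0.11" for oCEE and tE2 and "a variance of 2.09 for the random intercept, a variance of 0.03 for the random slope". Residual variance, time unit, missing-data rate and allocation are not stated, so 82% can be neither reproduced nor refuted. It is attainable. With five visits at 0, 1.5, 3, 4 and 7 years (sum of squares of time 28.2) and an assumed 164 per arm (492/3), SE = sqrt[2(0.03 + s²/28.2)/164]. At s² = 2.54 this is 0.0383; 0.11/0.0383 = 2.87, and Φ(2.87 - 1.96) is about 82% for tE2. For oCEE the matching s² is 10.34. The calculation concerns a linear rate of change only.

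**Inputs for the check.** From the plan: random-slope variance 0.03, six visits over 13 years, two-sided 5%. Assumed: the sixth visit at year 13 added to the five above, 164 per arm, complete data, residual variance s² of 0.5, 1 or 2.09.

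**Illustrative effect.** The arm difference grows by 0.11 a year to 0.44 at year 4, then falls in a straight line to 0 at year 13. At the six visits it is 0, 0.165, 0.33, 0.44, 0.293 and 0. The true difference in 13-year change is 0.

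**Linear model.** Sum of squares of time about its mean of 4.75: 109.875. Sum of (time - 4.75) × difference: 5.051 - 4.75 × 1.228 = -0.784. Expected slope difference: -0.784/109.875 = -0.0071 a year, or -0.09 over 13 years. SE = sqrt[2(0.03 + s²/109.875)/164].

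**Model with treatment by time-squared, time zero at baseline.** The expected treatment by time coefficient is 0.116, and the time-squared coefficient is -0.0092. The variation in time left after allowing for time-squared is 109.875 - 1469.44²/21279.47 = 8.40, so SE = sqrt[2(0.03 + s²/8.40)/164].

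| s² | SE, linear | z, linear | Rejects | SE, quadratic | z, treatment by time | Rejects |
|---|---|---|---|---|---|---|
| 0.5 | 0.0205 | -0.35 | 6.4% | 0.0330 | 3.5 | 94% |
| 1 | 0.0218 | -0.33 | 6.2% | 0.0426 | 2.7 | 78% |
| 2.09 | 0.0245 | -0.29 | 6.0% | 0.0583 | 2.0 | 51% |

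**Dependence on origin.** With time zero at year 13, the same coefficient becomes 0.116 + 26 × (-0.0092) = -0.123. If the 0.44 is instead held as a plateau, the coefficient is 0.114 with the origin at baseline and -0.052 with the origin at year 13. Neither is the 13-year difference of 0.44.

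**Type I error, simulated under no effect** (nominal 5%):
- One time form fixed in advance: 4.9 to 5.1%, including the visit-as-category contrast for change to year 13.
- Shape judged on trajectories pooled over arms: 5.0%.
- Quadratic model adopted when arm-specific curvature has p < 0.05, per contrast: 6.9 to 7.8% testing treatment by time alone, and 7.2 to 7.3% testing both terms jointly.
- Same rule, but the selected model is used to test the 13-year difference: 5.0 to 5.1%.
- Significance claimed on any linear or quadratic term, per contrast: 11.1 to 11.4%.

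These rates barely move across the residual variances tried.

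**Cost of naming the contrast.** SE of the visit-as-category difference in change to year 13 = sqrt[2(169 × 0.03 + 2s²)/164] = 0.272, 0.294, 0.336. Thirteen times the linear slope SE is 0.267, 0.284, 0.318. The ratios are 1.02, 1.03 and 1.06.

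**The case against.** The strongest reply is that a default exists. The model is treatment by time, the power calculation is for a rate of change, and looking at higher-order terms is an ordinary model check. Section 9.3 states the objective as longitudinal change, which a slope difference can answer. If time-squared enters only as a curve common to all arms, for ageing or practice, treatment by time remains a constant slope difference, and 13 times it is the 13-year difference. All of this stands. The shift in what is tested arises only if the squared term interacts with treatment, which the plan neither states nor rules out.

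Three stronger readings are tempting, and the documents do not support them.
- A reader might infer that the plan inflates type I error. That requires the choice of shape to respond to arm differences, and section 9.3 does not say the plots are split by arm. The 11% rate also needs a claim on any of several terms, which the plan does not describe. Any higher rate from adding a piecewise form rests on a model the plan never names.
- A reader might infer a large loss of power. The SE of treatment by time is 1.95 times larger in the quadratic model at s² = 1, which takes 80% power to 30%. This holds only if that lower-order coefficient alone decides the aim.
- A reader might infer that a real effect could be reversed. The fitted -0.09 over 13 years is about 0.3 SE from a true value of 0. In the plateau case the linear fit gives 0.38 for a true 0.44. These are modest errors.

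What the reply does not remove is the absence of a named deciding contrast once the model departs from linear.

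**Conclusion.** The point holds as a gap in specification with a practical consequence. The plan permits two models in which the test called treatment by time has expected z near -0.3 in one and 2.0 to 3.5 in the other, for an effect whose 13-year difference is zero. The second result would be read as an answer to Hypothesis 2 and is not one. This part does not depend on any inflation of error.

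Inflation is possible, not established: none if shape is judged on pooled arms, about 7-8% per contrast if arm-specific curvature triggers the quadratic model, and about 11% at the extreme.

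The sizes rest on the plan's slope variance and on assumed residual variance, equal arms, visit times and complete data. The washout pattern is an illustration, not a forecast.

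**What to change.** State in section 9.3, for each active arm versus placebo, one deciding contrast: the difference in change from baseline to year 13. Estimate it from a mixed model whose time form is fixed in advance. That can be visit as a category with treatment by visit, or one spline with a stated knot that uses actual elapsed time. Report the month-48 difference as a supporting contrast, and keep linear and other shapes as secondary description. Do any check of shape on trajectories pooled over arms.

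The cost is wording, plus a standard error about 2-6% larger than a straight-line fit if trajectories are truly linear and data are complete. Two limits should be addressed in the text. Visit as a category ignores variation in actual follow-up time, which the plan describes as only approximately 13 years. The precision cost may also differ when visits are missing, as the power section expects.

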10.4 MRI Image Analysis

10.4.1 Pre-processing to Correct Specific Artifacts: Several common forms of image

- imperfection can degrade the quality of the MR data we will collect. These are intensity in-homogeneity due to B1 receiver non-uniformity; drifts or discontinuities in gradient calibration over time; and gradient non-linearity. Image pre-processing operations designed to correct these effects are applied to each set of images prior to image processing.
- 10.4.2 MRI analysis of regional cortical structure: 3D Magnetization Prepared Rapid Acquisition Gradient-Echo (MPRAGE) developed for the multi-center ADNI study by the Mayo ADNI team, 107 will be used to provide optimal tissue contrast for brain morphology and is harmonized across Siemens, GE and Phillips scanners. We will investigate the AD-signature region of interest (ROI) that we previously identified in clinically diagnosed and autopsy-confirmed AD patients and tested for diagnostic reliability and accuracy. 108 We will investigate both hippocampus and dorsolateral prefrontal cortex volumes because preservation of these structures have been observed after estadiol treatment in ovariectomized animal models. 109 Furthermore. the preliminary data in Figure 6 suggest that dorsolateral prefrontal cortex volume is preserved in the tE2 group compared to placebo seven years after starting mHT in the KEEPS MRI sub-sample. We will use both publically available FreeSurfer 5.3^{110,111} and in-house atlas-based ROIs for the analysis of regional volumes adjusted for total intracranial volume (TIV). In addition, we will conduct a non-hypothesis based voxel based morphometry (VBM) analysis using Statistical Parametric Mapping 12 (SPM12),112 to explore regional differences between the mHT and placebo groups in the entire brain using an unbiased approach.

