slices with 2.5 x 2.5 mm in-plane resolution will be used. Subjects are instructed to remain awake with their eyes closed. This sequence was developed for the multicenter LEFFTDS and ARFL studies by the MCR team led by [name] and is harmonized across scanners. The images will be realigned correcting for head motion, and unwarped correcting for susceptibility-by-movement interactions, slice-time corrected, co-registered to T1-weighted image, normalized and smoothed using SPM12. After processing, we will examine connectivity within the default mode network using a seed-based approach, by using the BOLD time series for specific regions as a covariate of interest for whole brain regression analyses. ^{105,106} Each of the mHT group maps will be compared to placebo groups with SPM12.

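### Aim 3 runs about 60 unadjusted tests at P<.05 and names no cognitive domain or outcome version as the test of Hypothesis 3

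*Combined protocol and SAP*

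**What the plan says.** - **Decision rule (section 9.1):** "For each aim, all calculated P values will be 2-sided and P<.05 will be considered statistically significant".
- **Outcomes (section 9.4, Statistical Analysis for Objective 3):** "we will use the same cognitive factor scores and POMS as in Aim 2". Section 9.3 lists four factor scores, so with POMS counted once there are five measures.
- **Versions (same paragraph):** for each measure "we will consider the values at year 13, the changes in values from baseline to year 13", plus a predicted annual slope. That makes three versions.
- **Markers (same paragraph):** amyloid SUVR, white matter hyperintensities, AD-signature thickness and hippocampal volume. Primary Hypothesis 3 also lists tau (AV-1451), which the analysis paragraph omits.
- **Hierarchy:** Primary Hypothesis 3 marks amyloid as primary and speaks of longitudinal decline in cognitive performance. Section 1.1 and the wording of Objective 3 also include mood. No domain and no version is given priority.
- **Power (section 9.4):** "With 492 individuals and α =0.05", "we will have 80% power to detect Pearson correlation coefficients as small as 0.127", stated as equivalent to "an increase in the model R² due to the association of interest as small as 0.016".
- **Multiplicity:** the only multiple-comparison methods named (LSD, Tukey, Scheffé) are in section 9.2 and concern pairwise arm differences in Aim 1. None is named for Aim 3.

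**The concern.** A primary hypothesis should have a test that is identifiable before the data are seen. Here a reader cannot tell which result would decide Hypothesis 3. Making amyloid primary narrows the field to 15 results (five measures in three versions), each held to 0.05 by itself. One version, the year-13 value, is a cross-sectional level. A woman who scored low at randomization and did not change would count as low on it, so it does not address decline. The domain and version to emphasise could be chosen after the analysis, and the nominal 5% would not describe the error rate of the aim. The stated power is for a single unadjusted test and does not describe the planned set.

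**Working it through.** **1. The plan's own figure.** Inputs from section 9.4: N = 492, two-sided 0.05, 80% power. With Fisher's z:

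r = tanh[(1.960 + 0.842)/√(492 − 3)] = tanh(0.1267) = 0.126

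Power at r = 0.127 is 81%, and 0.127² = 0.016. The plan's figure reproduces, for one two-sided test without adjustment.

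**2. Number of tests.**
- All markers: 5 measures x 3 versions x 4 markers = 60. With tau: 5 x 3 x 5 = 75.
- Amyloid only: 5 x 3 = 15.
- Narrowest reading (amyloid, cognition only, change and slope only): 4 x 2 = 8.

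Covariate-adjusted models, the analyses with and without women who used hormone therapy after the trial, and any separate POMS indices would add to these counts.

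**3. Expected false positives if nothing is associated.** 60 x 0.05 = 3.0 (75 x 0.05 = 3.75 with tau). Correlation does not change this expectation.

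**4. Chance of at least one false positive.** Under independence it is 1 − 0.95^m: 95.4% for m = 60, 53.7% for m = 15 and 33.7% for m = 8. The documents give no correlations, so the other rows come from simulated correlated null z-statistics (40,000 draws) over assumed values.

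| Assumed correlations (measures / markers / versions) | 60 tests | 15 amyloid tests | 8 amyloid-by-change tests |
|---|---|---|---|
| Independent | 95% | 54% | 34% |
| 0.3-0.5 / 0.2-0.3 / 0.5-0.8 | 77-90% | 33-46% | 23-30% |
| 0.7 / 0.5 / 0.9 | 58% | 23% | 18% |

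**5. Effect of a Holm adjustment over four domains.** The first step is 0.05/4 = 0.0125, with critical value 2.498.
- Detectable r = tanh[(2.498 + 0.842)/√489] = 0.150; R² about 0.022.
- Power at r = 0.127: Φ(atanh(0.127) x √489 − 2.498) = Φ(2.824 − 2.498) = 63%.
- N for 80% power at r = 0.127: [(2.498 + 0.842)/0.1277]² + 3, about 687, against about 484 at 0.05. That is 42% more.

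**The case against.** - **The global null may not hold.** Section 2.5 describes a link between white matter hyperintensities and later mild cognitive impairment as established, and reports that hippocampal volume correlated with cognition in treated women in an earlier trial. A true association cannot be a false positive. This stands: expected false positives are 0.05 times the number of null tests, so 3 is the value when all 60 are null.
- **Hypothesis 3 is directional.** A result in the wrong direction would not support it, so the chance of false support is 2.5% per test. For the 8 narrow tests this gives 1 − 0.975^8 = 18% if independent and about 12-15% under the middle row of correlations. For the 15 amyloid tests the middle-row figure is 17-24%. This stands as a reduction, but section 9.1 is two-sided and these figures are still well above 2.5%.
- **The success rule is not spelled out.** Section 9.4 describes and measures associations; no sentence says that one P<.05 establishes Hypothesis 3. That is correct. But section 9.1 applies its rule to each aim without exception, and the Aim 3 power is set at that level.

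Two stronger readings are tempting. A reader might infer that a false finding is close to certain. That needs near-independence and no true association, yet the three versions are computed from the same scores. A reader might also infer that P<.05 is applied voxel by voxel to the brain maps. The documents do not say so. Section 10.4.2 says "we will conduct a non-hypothesis based voxel based morphometry (VBM) analysis", section 10.4.4 describes the fractional anisotropy analysis in similar exploratory terms, and section 10.4.5 says "Each of the mHT group maps will be compared to placebo groups with SPM12". None of these gives a threshold. They compare treatment groups and are not Aim 3 association tests. Their threshold is simply not stated.

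**Conclusion.** The concern holds for Aim 3. Following sections 9.1 and 9.4 as written leaves a primary objective with about 60 tests at 0.05, no designated domain or version, and one version that does not match the hypothesis. If every association is null, about 3 false positives are expected. The chance of at least one is about 58-95% for the full set, 23-54% for the primary marker and 18-34% on the narrowest reading. These ranges rest on assumed correlations, with independence at the upper ends. Even the lowest figure is more than three times the nominal 5%. The conclusion does not extend to the voxel-wise maps.

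**What to change.** In section 9.4:
- Name one longitudinal version as the test of Hypothesis 3, for example the model-based slope over 13 years. Saying only longitudinal change is not enough, because both the change from baseline and the slope would qualify.
- Test amyloid against the four cognitive domains on that version, with a Holm adjustment.
- Label the year-13 values, the other change version, mood and the other markers supportive, with FDR-adjusted values or no claim of significance. Add to section 9.1 that its P<.05 rule does not apply to these.
- Restate the power: at the first Holm step the detectable correlation is about 0.150 (R² about 0.022), and power at 0.127 is about 63%.

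The cost is SAP wording and some power. Power at the planned correlation falls from 81% to 63% at the first step. Restoring 80% would take about 687 women, practically all of the 688 that the Précis says will be invited, so the larger detectable correlation has to be accepted. Mood also leaves the confirmatory set although Objective 3 mentions it; Primary Hypothesis 3 in section 9.4 is limited to cognitive performance. Holm over four domains is one acceptable choice among several. What matters is that the choice is fixed before analysis.
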